absolute neutrophil count $\geq 1,000/\text{mcl}$
platelets $\geq 75,000/\text{mcl}$

hemoglobin ≥ 8.5 g/dL

Adequate hepatic function:

total bilirubin ≤ 2 mg/dL or ≤ 1.5 times ULN

AST(SGOT) & ALT (SGPT) ≤ 5 X ULN

INR ≤ 1.5 X ULN

Adequate renal function:

albumin ≥ 2.8 g/dL

creatinine ≤ 1.5 X ULN

16. Able to tolerate oral therapy.
17. Ability to understand and willingness to provide informed consent, and the willingness to comply with the requirements of the protocol. Informed consent may be obtained with the assistance of a medical translator according to institutional policies.
18. The effects of temsirolimus on the developing human fetus are unknown. For this reason and because sorafenib - also being used in this trial - is known to be teratogenic, women of child-bearing potential must have a negative pregnancy test within 14 days of study enrollment.

Also, women of child-bearing potential and men must agree to use two methods adequate contraception (hormonal plus barrier or two forms of barrier) or abstinence prior to study entry and for the duration of study participation. Should a woman become pregnant or suspect she is pregnant while she or her partner is participating in this study, she needs to inform her treating physician immediately. Men treated or enrolled on this protocol must also agree to use adequate contraception prior to the study, or be surgically sterile, for the duration of study participation, and for 3 months after completion of study drug administration.

19. Eligibility of patients receiving any medications or substances known to affect or with potential to affect the activity or pharmacokinetics of temsirolimus and/or sorafenib will be determined following review of the case by the Study Chair. Efforts should be made to switch patients who are taking enzyme-inducing anti-convulsant agents to other medications. A list of medications and substances known or with the potential to interact with selected relevant CYP450 isoenzymes, P-glycoprotein pathway, and/or UGT1A1 glucuronidation is provided in *Appendices 6-9*.

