The combination of temsirolimus and sunitinib resulted in dose-limiting toxicity. Dose-limiting toxicities (Grade 3/4 erythematous maculopapular rash, and gout/cellulitis requiring hospitalization) were observed in two out of three patients treated in the first cohort of a phase 1 study at doses of temsirolimus 15 mg IV per week and sunitinib 25 mg oral per day (Days 1-28 followed by a 2-week rest).

Administration of Vaccinations

The use of live vaccines and close contact with those who have received live vaccines should be avoided during treatment with temsirolimus. Examples of live vaccines are: intranasal influenza, measles, mumps, rubella, oral polio, BCG, yellow fever, varicella, and TY21a typhoid vaccines.

Use in Pregnancy

Pregnancy Category D. Temsirolimus administered daily as an oral formulation caused embryo-fetal and intrauterine toxicities in rats and rabbits at human sub-therapeutic exposures. Embryo-fetal adverse effects in rats consisted of reduced fetal weight and reduced ossifications, and in rabbits included reduced fetal weight, omphalocele, bifurcated sternabrae, notched ribs, and incomplete ossifications. In rats, the intrauterine and embryo-fetal adverse effects were observed at the oral dose of 2.7 mg/m²/day (approximately 0.04-fold the AUC in cancer patients at the human recommended dose). In rabbits, the intrauterine and embryo-fetal adverse effects were observed at the oral dose of ≥ 7.2 mg/m²/day (approximately 0.12-fold the AUC in cancer patients at the recommended human dose). Women of childbearing potential should be advised to avoid becoming pregnant throughout treatment and for 3 months after TORISEL[®] therapy has stopped. Temsirolimus can cause fetal harm when administered to a pregnant woman. If this drug is used during pregnancy, or if the patient becomes pregnant while taking this drug, the patient should be apprised of the potential hazard to the fetus. Men should be counseled regarding the effects of TORISEL[®] on the fetus and sperm prior to starting treatment. Men with partners of childbearing potential should use reliable contraception throughout treatment and are recommended to continue this for 3 months after the last dose of TORISEL[®].

Use in Breastfeeding

It is not known whether temsirolimus is excreted into human milk. Animal studies suggest potential for tumorigenicity for sirolimus (active metabolite of temsirolimus) in animal studies. Breastfeeding patients are excluded from this study.

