Patients with vascular diseases such as wet macular degeneration, vasculitis, or new peptic ulcer or other evidence of bleeding may receive the full dose of sorafenib but require close monitoring in accordance with established medical practice.

Cardiac Ischemia; Infarction

Physicians should also discuss with patients that cardiac ischemia and/or infarction has been reported during NEXAVAR® treatment, and that they should immediately report any episodes of chest pain or other symptoms of cardiac ischemia and/or infarction.

Infections

The data suggest that sorafenib has a mild lymphopenic effect with a small increase in the risk of infection. The effect of sorafenib on leukocyte count does not pose a significant safety concern.

Hypophosphatemia

Hypophosphatemia appears to be associated with sorafenib therapy. There were no instances of severe hypophosphatemia, defined as a serum phosphate value below 1.0 mg/dL, and there were no evident clinical manifestations associated with hypophosphatemia.

Neuropathy

Sorafenib was infrequently associated with peripheral neuropathy. The timing of these events suggests an inflammatory process rather than a cumulative neurotoxic effect.

Birth Defects, Fetal Loss, and Breastfeeding

Physicians should inform female patients that sorafenib may cause birth defects or fetal loss and that they should not become pregnant during treatment with sorafenib and for at least 2 weeks after stopping treatment. Both male and female patients should be counseled to use effective birth control during treatment with sorafenib and for at least 2 weeks after stopping treatment. Female patients should also be advised against breast-feeding while receiving sorafenib.

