- If treatment with either of the two study drugs is held for treatment-related toxicity for longer than 28 days (1 cycle), a patient should be removed from study.
- In selected cases where the investigator assesses the patient as having clinical benefit from protocol therapy, treatment may be resumed after > 28 day delay along with dose reduction, optimal supportive care, and close monitoring at the discretion of the treating investigator with the approval of the Study Chair.

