6.1.4 End-of-Treatment Study Procedures (within 60 days)

End-of-Treatment is defined as the day on which a decision is made by an investigator to discontinue a patient's participation in the study, often due to disease progression or toxicity, or by a patient to withdraw consent; this may also be referred to as the last day on study and may not necessarily coincide with the last day of protocol therapy, particularly if study drug has been held for toxicity.

- Complete physical examination, including height and weight measurement
- Vital signs, including temperature, blood pressure, heart rate, pain score, and oxygen saturation
- Update medical history
- Evaluation of clinical response or deterioration
- Evaluation of adverse events
- Concomitant medications
- ECOG Performance Status
- Child-Pugh class assessment
- Safety laboratory assessments: CBC w/ Diff, complete metabolic panel (electrolytes, BUN, creatinine, glucose, calcium, magnesium, phosphorus, total bilirubin, direct bilirubin, alkaline phosphatase, albumin, AST, and ALT), INR; serum AFP and HBV DNA quantitative by PCR should be measured if not done within 4 weeks
- If not done within preceding 8 weeks, imaging with CT chest (with or without contrast) plus triphasic CT abdomen and pelvis with intravenous contrast or triphasic gadolinium-enhanced MRI abdomen/pelvis to assess sites of known tumor using RECIST 1.1 measurements and to monitor for lung toxicity
- Banking of blood specimens if >4 weeks since specimens collected for banking

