8.6 Adverse Event Reporting to Funding Organization and Research Grant Provider

In addition to complying with all applicable regulatory reporting laws and regulations, each site will report the following information in writing to NCCN and research grant provider (Pfizer) in writing within 24 hours of the Investigator's awareness of occurrence. Principal Investigator should report SAEs as soon as they are determined to meet the definition, even if complete information is not yet available:

- a) a death, regardless of whether it is considered related to treatment with the Study Drug

- b) a non-fatal SAE that occurs during the reporting period and that is assessed by the Principal Investigator as both related to treatment with the Study Drug and unexpected for that product
- c) an SAE assessed by the Principal Investigator as related to the Study Drug that occurs after the SAE reporting period,
- d) an otherwise reportable event - Exposure During Pregnancy, Exposure During Lactation, Occupational Exposure, and Lack Of Effect. Even though there may not be an associated SAE, exposure to the Study Drug during pregnancy, exposure to the Study Drug during lactation, and occupational exposure to the Study Drug are reportable, and lack of effect of the Study Drug may also be reportable.

An event should be considered “related” to the Study Drug if a relationship is at least a reasonable possibility, and “unexpectedness” should be based upon a single safety reference document identified by the Principal Investigator and documented in association with the study.

Follow-up information regarding any of the above

- The participating investigator should include his or her assessment of the causal relationship between each SAE and the research grant provider’s product.
- Reports to NCCN will include the cover page provided (see Appendix J attached hereto), and reference Protocol Number NCCN-T12. Submit to NCCN via fax at [name] or via e-mail to [contact]
- Reports to Pfizer, Inc. will include the Reportable Event Fax Cover sheet (see Appendix 3.1) (use NCCN-T12 as the external reference number). Submit to the Pfizer U.S. Clinical Trial Department [REDACTED].
- A copy of the report should be sent to the coordinating center CRC

9. Statistical Considerations and Evaluation of Results

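### Inclusion criterion 18 gives women of child-bearing potential no contraception period after the last dose, although it gives men 3 months and section 4.1.1 advises women to avoid pregnancy for 3 months after temsirolimus

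*Combined protocol and SAP*

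**What the plan says.** Criterion 18 in section 3.3.1 sets contraception in two steps. The first covers women of child-bearing potential and men together: two adequate methods, or "abstinence prior to study entry and for the duration of study participation". The second covers men only and runs "for the duration of study participation, and for 3 months after completion of study drug administration". There is no matching second step for women. Between the two, the criterion deals with notification: "Should a woman become pregnant or suspect she is pregnant while she or her partner is participating in this study", she is to tell her treating physician at once.

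The drug sections give women periods after the last dose. For temsirolimus, section 4.1.1 states: "Women of childbearing potential should be advised to avoid becoming pregnant throughout treatment and for 3 months after" therapy ends. It recommends the same 3 months to men with partners of childbearing potential. For sorafenib, section 4.1.2 has physicians tell women that "they should not become pregnant during treatment with sorafenib and for at least 2 weeks after stopping treatment".

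Section 6.1.4 defines End-of-Treatment as the day on which participation is discontinued, and adds that "this may also be referred to as the last day on study and may not necessarily coincide with the last day of protocol therapy". Section 6.1.6 counts survival follow-up from study discontinuation. On reporting, section 8.6 says that "exposure to the Study Drug during pregnancy, exposure to the Study Drug during lactation, and occupational exposure to the Study Drug are reportable".

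**The concern.** Criterion 18 is what a patient agrees to and what a site checks at enrolment. As written, it binds the women in the trial to a shorter period than the men, and to a shorter one than the protocol advises for either drug. A site that follows it to the letter could let a woman stop contraception on her last day on study, well inside the 3 months in which section 4.1.1 advises against pregnancy.

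The notification instruction has the same limit. A pregnancy that begins after participation ends but within the 3 months falls outside it. This includes a pregnancy in the partner of a male patient who is himself still within his required 3 months. Section 8.6 makes exposure during pregnancy reportable, but a site can report only what it is told. The visit schedule gives no second check, because Table 6.1 lists a pregnancy test at screening only.

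The possible harm is to a fetus and could not be undone. Section 4.1.1 classes temsirolimus as Pregnancy Category D, and criterion 18 itself treats sorafenib as a known teratogen.

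**Working it through.** The plan states no figure to reproduce. The check sets the texts side by side and then sizes the gap.

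**Periods after the last dose**

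| Source | Women | Men |
|---|---|---|
| Criterion 18 (must agree) | none stated | 3 months |
| Section 4.1.1, temsirolimus (advice) | 3 months | 3 months |
| Section 4.1.2, sorafenib (advice) | at least 2 weeks | at least 2 weeks |

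For the combination the longer period, 3 months, should govern. The men's 3 months were carried from section 4.1.1 into criterion 18; the women's were not, and no reason is given.

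**Does study participation already cover the 3 months?** Three places say no.
- Section 6.1.4 ends participation on the day of the decision to discontinue.
- Section 6.1.6 counts the survival follow-up of up to 5 years from study discontinuation, so that follow-up comes after participation.
- Criterion 18 lists the men's 3 months in addition to participation, which would be unnecessary if participation included follow-up.

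**Size of the gap**

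Uncovered days = 3-month window − days from last temsirolimus dose to last day on study.

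Window: 3 × 365.25 / 12 = 91.3 days (13.0 weeks).

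The documents do not give the lag, so I assumed three values. The weekly schedule is in section 5.1. The hold limit is in section 5.3: if either drug is "held for treatment-related toxicity for longer than 28 days (1 cycle), a patient should be removed from study".

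| Assumed lag | Calculation | Uncovered |
|---|---|---|
| Removed on the day of the last dose | 91.3 − 0 | 91.3 days (13.0 weeks) |
| Removed one weekly interval later | 91.3 − 7 | 84.3 days (12.0 weeks) |
| Removed after a 28-day hold, 7 + 28 = 35 days | 91.3 − 35 | 56.3 days (8.0 weeks) |

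A longer hold, which section 5.3 allows with Study Chair approval, would shorten the gap further.

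**A more generous reading.** Section 6.1.4 allows the End-of-Treatment procedures within 60 days. If participation is taken to run to that visit at its latest, the gap is 91.3 − 60 = 31.3 days with no lag and 31.3 − 7 = 24.3 days with a one-week lag. After a 35-day lag there is none, since 60 + 35 = 95 exceeds 91.3. Cover then depends on when the visit happens to fall.

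**The case against.** The strongest reply is that the safety information is already in the protocol. Section 4.1.1 gives women the 3-month advice and section 4.1.2 adds the sorafenib counselling, so a site that reads the whole document would pass both on. The consent form, the usual place for such an instruction, is not in the review copy and may state 3 months. This limits what can be said about what patients are told in practice. It does not remove the mismatch: section 4 is counselling text, while criterion 18 is the commitment a woman gives to enter the trial.

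A second reply is that study participation is not formally defined. Toxicity follow-up continues under section 6.1.5 and survival follow-up for up to 5 years under section 6.1.6. If participation included the latter, the gap would be zero. The redundancy argument from the men's sentence is not decisive either, since that sentence repeats other requirements already placed on men. These points are fair, but sections 6.1.4 and 6.1.6 favour the narrow reading, and the broad one would require two methods or abstinence for up to 5 years. Either reading calls for a stated end date.

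Third, section 8.6 does not tie its pregnancy item to time on study, so the site's own reporting duty is not shortened. That stands. The documents also do not settle whether a conception after the last dose counts as exposure during pregnancy. What remains is that criterion 18 stops asking the woman to tell anyone.

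Fourth, the day counts rest on assumed lags. That is correct; they show the range and are not estimates.

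**Conclusion.** The concern holds. Criterion 18 sets no period after the last dose for women of child-bearing potential, against 3 months for men in the same criterion and 3 months advised for women in section 4.1.1. The uncovered time is about 8 to 13 weeks under the assumed lags of 35 to 0 days. It would be about 31 days or less if participation were stretched to the latest End-of-Treatment visit. The conclusion rests on reading participation as ending at study discontinuation.

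Two things cannot be settled from the documents: how many of the 25 to 28 patients are women of child-bearing potential, and what the consent form says. The matter is one of patient safety and internal consistency. It has no bearing on the sample size, the error rates or the primary analysis.

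**What to change.** In criterion 18:
- Require women of child-bearing potential to continue contraception until 3 months after the last dose of study drug. This also satisfies the 2-week minimum for sorafenib.
- Extend the instruction to notify the treating physician of a pregnancy to the same date, for women in the trial and for partners of men in the trial.
- Leave the men's 3-month period unchanged.

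Then check that the consent form says the same.

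The cost is one or two lines of protocol text and the consent-form check. No visit, test, design feature or analysis changes. When the criterion is edited, its opening sentence on fetal effects of temsirolimus could be aligned with section 4.1.1; that is clerical and alters no procedure.

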3.3.2 Exclusion Criteria

1. Biliary tract cancers or fibrolamellar variant tumors are excluded.
 - a. Cases with mixed, composite, or combined HCC-cholangiocarcinoma histology are eligible with approval from study chair and provided the treating investigator believes it is in the best interest of the patient to treat the tumor with therapy targeted towards the HCC component of tumor based upon review of pathology and clinical characteristics
2. Prior systemic or antiangiogenic therapy for HCC (including thalidomide, sorafenib, sunitinib, or bevacizumab). Prior systemic therapy for other diagnoses is permitted if greater than 6 months have elapsed since last dose, any prior toxicity has recovered to \leq grade 1 by CTCAE v4.0, and treatment was not discontinued for toxicity.
3. Prior treatment with mTOR inhibitor or other molecularly targeted therapy.

4. Prior systemic cytotoxic therapies for HCC (chemoembolization is permitted if inclusion criteria are met).
5. Treatment with other investigational agents.
6. Immunosuppressive medications including systemic corticosteroids unless used for adrenal replacement, appetite stimulation, acute therapy for asthma or bronchitis exacerbation (≤ 2 weeks), or antiemesis
7. Patients with known HIV infection are ineligible due to risk of pharmacokinetic interactions between anti-retroviral therapy and the study drugs, as well as potential for significant immunosuppression and serious infections with mTOR inhibition.
8. Patients who have undergone liver transplantation are excluded.
9. Uncontrolled hypertension ($> 150/90$ mmHg).
10. Uncontrolled hyperlipidemia (total cholesterol > 350 or triglycerides > 300).
11. Symptomatic brain or bone metastases; prior radiation and/or steroid therapy for brain or bone metastases (if applicable) must be completed ≥ 2 weeks prior to study enrollment.
12. History of seizure disorder requiring antiepileptic medication or brain metastases with seizures.
13. Serious non-healing wound, ulcer, bone fracture, or abscess.
14. Major surgical procedure less than 4 weeks from start of protocol treatment.
15. Patients requiring chronic anticoagulation with warfarin are excluded. Patients treated with low molecular weight heparin or unfractionated heparin are eligible if on a stable dose without evidence of clinically significant bleeding for at least 2 weeks prior to enrollment.
16. Active second malignancy other than non-melanoma skin cancer or cervical carcinoma in situ. (Patients with history of malignancy are not considered to have a "currently active" malignancy if they have completed therapy and are now considered by their physician to be at less than 30% risk for relapse.)
17. Uncontrolled intercurrent illness including, but not limited to: Ongoing or active infection, symptomatic congestive heart failure, unstable angina pectoris, uncontrolled cardiac arrhythmia, uncontrolled peripheral vascular disease, myocardial infarction within preceding 12 months, cerebrovascular accident within preceding 12 months, pulmonary disease impairing functional status or requiring oxygen, impairment in gastrointestinal function that may affect or alter absorption of oral medications (such as malabsorption or history of gastrectomy or bowel resection).
18. Patients will be excluded if there is any history of allergic reaction(s) attributed to compounds of similar composition to temsirolimus, sorafenib, their metabolites, or any component of their formulation (including excipients and polysorbate 80). This includes hypersensitivity to macrolide antibiotics due to potential for cross-reactivity with temsirolimus.
19. Pregnant or lactating women are excluded from this study because temsirolimus and sorafenib are drugs with the potential for teratogenic or abortifacient effects. Because there is an unknown but potential risk for adverse events in nursing infants secondary to treatment

of the mother with temsirolimus or sorafenib, breastfeeding should be discontinued if the mother is receiving temsirolimus/sorafenib treatment.

20. Patients who require prohibited medications with potential for serious interactions with protocol therapy, and who cannot have therapeutic substitution are excluded. Patients receiving any medications or substances that are inhibitors or inducers of CYP450 enzyme(s) are ineligible. Lists of prohibited medications and substances known, or with the potential to interact with the specified CYP450 enzyme(s) isoenzymes are provided in *Appendices 6-9 Prohibited Medications*
21. Psychiatric illness, other significant medical illness, or social situation which, in the investigator's opinion, would limit compliance or ability to comply with study requirements.

3.4 Duration of Therapy

In the absence of treatment delays due to adverse events, individual patient treatment may continue indefinitely, or until:

- Disease progression by RECIST 1.1 or clinically
- Inter-current illness that prevents further administration of treatment
- Unacceptable adverse event(s) toxicity, or unmanageable toxicity despite optimal supportive care and dose modifications (*Section 5 Treatment Plan*)
- Patients decides to withdraw from the study or is unable to comply with study procedures
- General or specific changes in the patients' condition, or other factors which may influence safety or compliance, that render the patient unacceptable for further treatment in the judgment of the investigator

When a patient is discontinued from the study, the reason(s) for discontinuation will be documented in study records.

